#### 6.5.1. Withdrawal from treatment

Patients will be withdrawn from treatment in the case of:

- Recurrence or occurrence of a secondary malignancy. Investigators are encouraged
  to await the result of the IRC assessment before making treatment decisions unless
  clinical considerations require immediate intervention eg, in the case of brain
  metastases;
- Unacceptable toxicity;
- Need for anticancer therapy not specified in the protocol;
- Congestive heart failure;
- Repeated noncompliance;
- Patient becomes pregnant;
- Patient lost to follow-up;
- Patient choice to withdraw from treatment (follow-up permitted by patient)

If patients require >2 consecutive weeks of dose interruption, a discussion should be made in consultation with the medical monitor.

Data to be collected for the end of study treatment/withdrawal from treatment are described in the End of Study Treatment/Withdrawal from treatment Procedures section (Section 6.2.3). Patients will be followed up for at least 28 days after the last dose of study drug for adverse events and concomitant medications and treatments

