**7.5.1. Adverse Events**

Adverse event (AE) terms recorded on the CRF will be mapped to PT and SOC using the Medical Dictionary for Regulatory Activities (MedDRA). The severity of AEs will be evaluated by the investigator by employing the CTCAE v4.03 (Cancer Terminology Criteria for Adverse Events). The investigator will also judge each event to be “not related” or “related” to study treatment.

A TEAE is defined as any AE with an onset date on or after the date of the first dose of study treatment or any ongoing event on the date of the first dose of study treatment that worsens in severity after the date of the first dose of study treatment.

The AE observation period is defined as the time from date of the first dose of study treatment until 28 days after the last dose of study drug is administered. TEAEs with an onset date through the end of the study observation period will be summarized by treatment arms. The Grade 5 TEAEs with onset date outside of the observation period may be tabulated separately.

For summaries of subject incidence of TEAE, at each level of summarization, a subject will be counted only once for each AE preferred term experienced by the subject within that level (i.e., multiple episodes of events with the same preferred terms will be counted only once). Selected summaries of subject-incidence of AEs (as defined in Section 7.5.1.2) will include the risk difference (defined as the proportion with the event in the axitinib arm minus the proportion with the event in the placebo treatment arm) with 95% CIs and the risk ratio (or relative risk; defined as the proportion with the event in the axitinib group divided by the proportion with the event in the placebo group) with 95% CIs. An overall summary of treatment emergent adverse events (including those that stopped more than 28 days after the decision to discontinue study treatment) will be provided with the number and percent of subjects who experienced the following in each treatment group:

- Subjects with a TEAE
- Subjects with a Related TEAE
- Subjects with a Serious TEAE at any time (including active treatment period plus follow-up period)
- Subjects with a Serious Related TEAE
- Subjects with a Worst-Grade of  $\geq 3$  TEAE
- Subjects with a Worst-Grade of  $\geq 3$  Related TEAE
- Subjects with a Grade 5 TEAE at any time

---

|           |   |                 |           |
|-----------|---|-----------------|-----------|

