**7.5.1.2 Treatment Emergent Adverse Events of Special Interest**

The following TEAEs of special interests will be summarized for the as-treated population and by SOC and PT for each categorized treatment group. The list of MedDRA defined SOC and PTs for TEAEs of special interest are provided below and may be updated at the time of database lock based on the MedDRA version in use at the time of reporting and/or any additional safety information available from the Axitinib program that may determine a need to consider additional events of interest. Additionally, for the following special adverse events, Kaplan-Meier methods will be used to display the time to the first occurrence of each of these 13 event categories, if the number of events is  $\geq 10$  events per treatment arm:

| Adverse Events of Special Interest | Search Terms (MedDRA version 20.1)  |
|---|--|
| Cardiac disorders                         | Cardiac disorders – SOC
Cardiac and vascular investigations (excluding enzyme tests)- HLGT  |
| Nervous system disorders                  | Central nervous system vascular disorders- HLGT  |
| Vascular disorders                        | Embolism and thrombosis- HLGT
Pulmonary Embolism PT   |
| Renal vascular disorders                  | Renal vascular and ischaemic conditions (HLT)
Renal failure and impairment (HLT)
Renal hypertension and related conditions (HLT) |

Document: C:\Users\q764206\AppData\Local\Microsoft\Windows\Temporary Internet Files\Content.Outlook\GWW33WM3\ATLAS\_SAPFinal v8.0\_06MAR2018.docx  
 Author: [name] (Updated [name]; [name]; [name], [name]) Version Number: Final 8.0

Version Date: 06MAR2018

Template No: CS\_TP\_BS016 – Revision 2 Reference: CS\_WI\_BS005  
 Effective Date: 01Feb2010

Statistical Analysis Plan

|   |   |
|---|---|
| Haemorrhage                                 | Haemorrhage (excluding lab terms) SMQ (broad and narrow) and Haemorrhage laboratory terms SMQ (broad and narrow)  |
| Hypertension                                | Hypertension SMQ narrow   |
| Proteinuria                                 | MedDRA PTs: Albumin urine present, Proteinuria, Protein urine, and Protein urine present  |
| Thyroid Dysfunction                         | Thyroid dysfunction SMQ broad   |
| Venous Embolic and Thrombotic Events (VTE)  | Embolic and thrombotic events, venous SMQ narrow  |

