| Palmar-Plantar Erythrodysesthesia (PPE)     | MedDRA PTs: Palmar-plantar erythrodysesthesia syndrome, palmar erythema, and plantar erythema.  |
| Fatigue and Asthenic Conditions             | MedDRA PTs: Asthenia, Autonomic nervous system imbalance, Decreased activity, Listless, Sluggishness, Chronic fatigue syndrome, Fatigue and Malaise)  |
| Hepatic Disorders                           | Cholestasis and jaundice of hepatic origin (SMQ narrow)
Drug-related hepatic disorders - comprehensive search (SMQ narrow)
Liver related investigations, signs and symptoms (SMQ narrow)
Hepatic & Hepatobiliary disorders (HLGT)  |
| Congestive Heart Failure/Cardiomyopathy     | MedDRA PTs: Acute left ventricular failure, Acute right ventricular failure, Cardiac failure, Cardiac failure acute, Cardiac failure chronic, Cardiac failure congestive, Cardiac failure high output, Cardiogenic shock, Cardiopulmonary failure, Chronic left ventricular failure, Chronic right ventricular failure, Cor pulmonale, Cor pulmonale acute, Cor pulmonale chronic, Ejection fraction decreased, Left ventricular failure, Low cardiac output syndrome, Neonatal cardiac failure, Right ventricular failure, Ventricular failure, Cardiac output decreased, Cardio-respiratory distress, Central venous pressure increased, Diastolic dysfunction, Left ventricular dysfunction, Myocardial depression, Oedema due to cardiac disease, Right ventricular dysfunction, Systolic dysfunction, Ventricular dysfunction, Cardiomyopathy acute, Congestive cardiomyopathy, Ejection fraction abnormal, Ejection fraction decreased. |
| Carcinogenicity (Second Primary Malignancy) | SMQ malignant or unspecified tumours, SMQ Malignant tumours, SMQ Tumours of unspecified malignancy and the Lower Level Term (LLT): Secondary primary malignancy.  |

For Cardiovascular disorders: Include Cardiac disorders, Nervous system disorders, Vascular disorders

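### The search list for Congestive Heart Failure/Cardiomyopathy in SAP 7.5.1.2 omits the unqualified term that names the category, so an event coded to that term would not be counted in it

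*SAP*

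**What the plan says.** The table in SAP 7.5.1.2 gives each special-interest category its own search terms, under MedDRA version 20.1. The row "Congestive Heart Failure/Cardiomyopathy" is defined by individual preferred terms only, starting "MedDRA PTs: Acute left ventricular failure, Acute right ventricular failure, Cardiac failure, Cardiac failure acute, Cardiac failure chronic, Cardiac failure congestive". It has no standardised query or higher-level term that would bring in a term not on the list. The two places where *Ejection fraction decreased* occurs are "Cor pulmonale chronic, Ejection fraction decreased, Left ventricular failure" and the end of the row, "Cardiomyopathy acute, Congestive cardiomyopathy, Ejection fraction abnormal, Ejection fraction decreased".

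SAP 7.5.1 then says how these categories are used: "Selected summaries of subject-incidence of AEs (as defined in Section 7.5.1.2) will include the risk difference", together with the risk ratio, each with a 95% confidence interval. SAP 7.5.1.2 adds a Kaplan-Meier display of time to first occurrence, on condition that there are at least 10 events per arm. The same section allows for revision: the lists "may be updated at the time of database lock based on the MedDRA version in use at the time of reporting", or in response to further safety information from the axitinib program.

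A separate category is defined by "Cardiac disorders – SOC" plus a group of cardiac and vascular investigation terms.

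**The concern.** The category title names two conditions. The heart failure half has its own term on the list, *Cardiac failure congestive*. The cardiomyopathy half has only two qualified terms, *Cardiomyopathy acute* and *Congestive cardiomyopathy*. A programmer who applies the list as written will not retrieve an event coded to plain *Cardiomyopathy*, although that is the category's own name.

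At stake is the between-arm summary of one of the harms that the trial singles out. If the category turns out to have few cases, one or two that are missed can visibly move its risk difference and risk ratio. The matter may also arise before database lock. SAP 6.3 bases the interim safety presentation and the regular Data Monitoring Committee reviews on Section 7.5, so if those outputs include the special-interest tables, the committee would see the category with the gap in it.

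**Working it through.** The plan states no figure on this point to reproduce. The check is a count of the list, a comparison within the table, and simple arithmetic on the possible effect.

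**Step 1. Count the list.** Splitting the row at its commas gives 34 entries. *Ejection fraction decreased* is entry 15 and again entry 34, so the distinct terms number 34 − 1 = 33. Two entries contain the word cardiomyopathy (entries 31 and 32). None is the plain term.

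**Step 2. Compare within the row.** Five entries carry the qualifier acute. Four of them have their unqualified counterpart on the list:

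| Qualified entry | Unqualified counterpart on the list? |
|---|---|
| Acute left ventricular failure | Yes |
| Acute right ventricular failure | Yes |
| Cardiac failure acute | Yes |
| Cor pulmonale acute | Yes |
| Cardiomyopathy acute | No |

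**Step 3. Compare with the other rows.** The other rows defined only by preferred terms are Proteinuria, Palmar-Plantar Erythrodysesthesia, and Fatigue and Asthenic Conditions. Each contains the term that names it: *Proteinuria*; *Palmar-plantar erythrodysesthesia syndrome*; *Fatigue* and *Asthenia*. The cardiomyopathy half of this row is the exception, and the SAP gives no reason for it.

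**Step 4. Size per missed case.** About 700 subjects are randomized 1:1 (Protocol 3), which is 700 / 2 = 350 per arm. The as-treated population may be slightly smaller. One missed case lowers that arm's incidence by 1 / 350 = 0.29 percentage points.

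**Step 5. Range of effect on the comparison.** The documents give no expected counts, so the counts below are assumptions chosen only to show how the result can move. The risk difference is (axitinib cases − placebo cases) / 350. The risk ratio is axitinib cases / placebo cases.

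| Assumed pattern | All cases (axitinib vs placebo) | Counted by the list | Risk difference, points | Risk ratio |
|---|---|---|---|---|
| No event coded to the plain term | 4 vs 1 | 4 vs 1 | 0.86, unchanged | 4.0, unchanged |
| Half the cases missed in each arm | 4 vs 2 | 2 vs 1 | 0.57 to 0.29 | 2.0, unchanged |
| Two missed, axitinib only | 4 vs 1 | 2 vs 1 | 0.86 to 0.29 | 4.0 to 2.0 |
| One missed, placebo only | 4 vs 2 | 4 vs 1 | 0.57 to 0.86 | 2.0 to 4.0 |

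The effect can be zero, and when it is not, its direction is not fixed.

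**The case against.** The strongest reply is that little is lost. SAP 7.5.1.2 summarizes the special-interest events by system organ class and preferred term. A plain *Cardiomyopathy* event in the Cardiac disorders class would therefore have its own line, by arm, in the Cardiac disorders category. Protocol 9.4.1 also tabulates all treatment-emergent events by preferred term and lists all adverse event data by patient. SAP 7.5 plans no formal safety comparison, and the lists can be updated at database lock. All of this stands, and it limits the point to one category's total and the estimates built on it. The update clause, however, is optional, and neither of its stated triggers is the correction of an omission.

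A reader might infer more than the documents support:

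- **That such an event disappears from safety reporting, or is lost among other cardiac terms.** It does not. It stays visible by preferred term, as above.
- **That sites would most likely report the unqualified term.** Nothing in either document shows this. Nor do they show that *Cardiomyopathy* is a separate preferred term in MedDRA 20.1.
- **That the duplicate inflates counts, or took the place of the missing term.** SAP 7.5.1 counts a subject once per preferred term, so the duplicate is harmless to counts. What was meant in its place is a guess.
- **That the time-to-event display is affected in any case.** It is produced only with at least 10 events per arm. At counts like those assumed above there would be no display.
- **That the withdrawal rule makes the gap more serious.** Protocol 6.5.1 lists "Congestive heart failure" as a reason to withdraw from treatment, but that condition is covered by *Cardiac failure congestive*. It has no bearing on the cardiomyopathy gap.

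**Conclusion.** The point holds as a small defect in a stated retrieval rule. The category's closed list lacks the unqualified term that names half of it. If an event is coded to that term, the event is left out of the category's incidence and of any risk difference and risk ratio derived from it.

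The size is zero if no event is so coded, and otherwise about 0.29 percentage points of an arm's incidence per missed case. The Kaplan-Meier display comes into play only if each arm reaches 10 events. The primary analysis, the alpha allocation and the stopping rules are untouched.

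The conclusion rests on three assumptions: that *Cardiomyopathy* is a preferred term in the MedDRA version used, that at least one event is coded to it, and that about 350 subjects per arm are treated. The documents cannot settle the first two, so the consequence is conditional. The omission and the duplicate can be read directly from the SAP. This is worth correcting but is not a serious flaw.

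**What to change.** Before unblinding, check the list for this row in SAP 7.5.1.2 against the MedDRA version in use. Add *Cardiomyopathy* if it is a preferred term there, and delete the second *Ejection fraction decreased*. The list would then have 34 entries, all distinct. If the plain term was left out on purpose, say so and give the reason.

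The correction should be made now and not left to the optional update at database lock, because a safety definition changed after unblinding is less credible than one fixed beforehand. The cost is one line of SAP wording and the matching line in the program. No additional data are needed.

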## 5.3.4.1. Management of Axitinib/Placebo-Related Adverse Events

This section contains management of adverse events except hypertension and proteinuria which are discussed in subsequent sections.

The criterion for dose modification for study-drug-related adverse events is summarized in the table below:

Table 3 Criteria for Dose Modification for Axitinib/Placebo – Related Adverse Events Other Than Hypertension Or Proteinuria

Related Adverse Events	Intervention
Grade 1	Continue at same dose level.
Grade 2*	Continue at same dose level or decreased dose to one
	lower dose level. a)
Grade 3*	Interrupt dosing; re start at one or two lower dose level
	as soon as improvement to CTCAE Grade ≤1 or
	baseline. b) Discontinue dosing in case of grade 3
	persisting for $\geq 2$ weeks or grade 3 despite dose
	reduction to 1 mg BID.
Grade 4 or RPLS**	Discontinue dosing

\* Patients who have a grade 3 arterial event, grade 3 hemorrhagic event, grade 3 perforation/fistula, grade 3 palmar-planter erythrodysesthesia syndrome (PPE), or persistent grade 2 PPE despite dose reduction to 1 mg BID, should be discontinued dosing.

- a) Dose may be decreased to one lower dose level if the investigator considers it is difficult to continue treatment at same dose level.
- b) Dose may be decreased to two lower dose level if the investigator considers it is difficult to continue treatment at one lower dose level.

\*\* Treatment interruption for patients with signs/symptoms of reversible posterior leukoencephalopathy (RPLS). RPLS is a neurological disorder which can present with headache, seizure, lethargy, confusion, blindness and other visual and neurologic disturbances. Mild to severe hypertension may be present. Magnetic resonance imaging is necessary to confirm the diagnosis of RPLS. In case of confirmed diagnosis discontinue permanently.

Dose may also be interrupted or decreased at the discretion of the investigator even if none of the above criteria applies.

Guidelines for dose reductions for specific adverse events are provided in the following sections.

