#### 8.3. Definition of an Adverse Event

An adverse event is any untoward medical occurrence in a clinical investigation patient administered a product or medical device; the event need not necessarily have a causal relationship with the treatment or usage. Examples of adverse events include but are not limited to:

- Abnormal test findings;
- Clinically significant symptoms and signs;
- Changes in physical examination findings;
- Hypersensitivity;

Additionally, they may include the signs or symptoms resulting from:

- Drug overdose;
- Drug withdrawal;

- Drug abuse;
- Drug misuse;
- Drug interactions;
- Drug dependency;
- Exposure In Utero.

Worsening of signs and symptoms of the malignancy under trial should be reported as adverse events in the appropriate section of the CRFs. Disease progression assessed by measurement of malignant lesions on radiographs or other methods should not be reported as adverse events. See description of Serious Adverse Events in Section 8.5 with respect to disease progression.

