#### 8.5. Serious Adverse Events

A serious adverse event or serious adverse drug reaction is any untoward medical occurrence at any dose that:

- Results in death;
- Is life-threatening (immediate risk of death);
- Requires inpatient hospitalization or prolongation of existing hospitalization;
- Results in persistent or significant disability/incapacity;

• Results in congenital anomaly/birth defect.

Progression of the malignancy under trial (including signs and symptoms of progression) should not be reported as a serious adverse event unless the outcome is fatal during the trial or within the safety reporting period. Hospitalization due to signs and symptoms of disease progression should not be reported as serious adverse event. If the malignancy has a fatal outcome within the safety reporting period, then the event leading to death must be recorded as an adverse event and as a serious adverse event with CTCAE Grade 5 (See Section 8.7, Severity Assessment). Any histopathologically confirmed secondary malignancy must be reported as SAE.

Medical and scientific judgment should be exercised in determining whether an event is an important medical event. An important medical event may not be immediately life-threatening and/or result in death or hospitalization. However, if it is determined that the event may jeopardize the patient and/or may require intervention to prevent one of the other outcomes listed in the definition above, the important medical event should be reported as serious.

Examples of such events are intensive treatment in an emergency room or at home for allergic bronchospasm; blood dyscrasias or convulsions that do not result in hospitalization; or development of drug dependency or drug abuse.

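### The search for second primary malignancies does not exclude the renal cancer under study, so in-window RCC deaths coded to a tumour term would be counted as second primaries

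*SAP*

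**What the plan says.** **The search.** The table of special-interest events in SAP 7.5.1.2 has a row for carcinogenicity, labelled as second primary malignancy. Its search terms are "SMQ malignant or unspecified tumours, SMQ Malignant tumours, SMQ Tumours of unspecified malignancy" together with one lower-level term for secondary primary malignancy. No exclusion is stated.

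**What enters the adverse event data.**
- Protocol 8.5, on the study disease: "If the malignancy has a fatal outcome within the safety reporting period, then the event leading to death must be recorded as an adverse event". The same sentence makes it a serious adverse event of CTCAE Grade 5.
- Protocol 8.3, on non-fatal progression: "Disease progression assessed by measurement of malignant lesions on radiographs or other methods should not be reported as adverse events".
- Protocol 8.5, on true second primaries: "Any histopathologically confirmed secondary malignancy must be reported as SAE".

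**The window.** SAP 7.5.1 defines the adverse event observation period as the "time from date of the first dose of study treatment until 28 days after the last dose of study drug is administered". Protocol 8.2 ends routine reporting of serious events at the same 28 days.

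**What is produced from the row.** SAP 7.5.1 attaches risk differences and risk ratios with 95% confidence intervals to the events defined in 7.5.1.2. SAP 7.5.1.2 adds a breakdown by system organ class and preferred term. It also plans a Kaplan-Meier display of time to first occurrence for "each of these 13 event categories", provided there are at least 10 events per arm.

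**The concern.** The row's label and its search do not describe the same events. The label promises cancers other than the one being treated. The search, judged by the names of its queries, collects any malignant or unspecified tumour, and Protocol 8.5 supplies one route by which the study cancer reaches the adverse event database.

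A new-cancer signal for a drug given for up to three years to patients with no evidence of disease is likely to rest on few cases, so a few misclassified deaths could change it. If the misclassified deaths fall equally on the two arms, they pull the risk ratio towards 1. If they fall more on placebo, they pull it further down and can make an even split of true second primaries look protective. The breakdown by preferred term would let a reader see an RCC term, but it would not correct the row total, its risk ratio or its curve.

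**Working it through.** The plan gives no figure for this row, so there is nothing to reproduce. The check has three steps.

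**Step 1. Can a study-disease case meet the search?**

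| Type of case | In the adverse event data? | Retrieved as a second primary? |
|---|---|---|
| Non-fatal RCC recurrence found on imaging | No (Protocol 8.3) | No, unless misreported |
| RCC fatal within the reporting period | Yes, Grade 5 (Protocol 8.5) | Yes, if coded to a tumour term |
| RCC fatal after the window | Generally no (Protocol 8.2, SAP 7.5.1) | Generally no |
| Histologically confirmed second primary | Yes, as a serious event (Protocol 8.5) | Yes, as intended |

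The second line is the defect. That the queries contain RCC terms is inferred from their names, because MedDRA content is not in the documents.

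**Step 2. How far can the row's risk ratio move?** All counts here are assumed, because the documents give none. Take 350 patients per arm (about 700 randomized 1:1), true second primaries *a* on axitinib and *p* on placebo, and misclassified RCC deaths *f_a* and *f_p* in different patients.

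- Risk ratio = (a + f_a) / (p + f_p)
- SE of log risk ratio = √[1/x − 1/350 + 1/y − 1/350], where x = a + f_a and y = p + f_p
- Risk difference = (x − y) / 350

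With no misclassification and 10 v 5, the ratio is 10/5 = 2.00. The SE is √(0.1000 + 0.2000 − 0.0057) = 0.542, so the 95% CI is exp(0.693 ± 1.96 × 0.542) = 0.69 to 5.79.

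| RCC deaths added (axitinib v placebo) | Row count | Risk ratio (95% CI) | Risk difference |
|---|---|---|---|
| 0 v 0 | 10 v 5 | 2.00 (0.69 to 5.79) | 1.43% |
| 1 v 2 | 11 v 7 | 1.57 (0.62 to 4.01) | 1.14% |
| 2 v 4 | 12 v 9 | 1.33 (0.57 to 3.12) | 0.86% |
| 4 v 8 | 14 v 13 | 1.08 (0.51 to 2.26) | 0.29% |

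With 7 v 7 true second primaries, the same additions move the ratio from 1.00 to 8/9 = 0.89, 9/11 = 0.82 and 11/15 = 0.73.

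**Step 3. Does this depend on the assumed 1:2 split?** The row's ratio always lies between the true ratio a/p and the ratio of added cases f_a/f_p. It falls whenever the added cases are less tilted to axitinib than the true ones.
- Equal addition, 3 v 3: 13/8 = 1.63. The risk difference stays at 5/350 = 1.43%.
- Addition in proportion to the design hazard ratio of 0.654, used only as a guide because it refers to disease-free survival (DFS): 5 placebo deaths go with 5 × 0.654 ≈ 3 on axitinib, giving 13/10 = 1.30.
- No addition: no change.

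The added cases also narrow the interval, whose upper limit falls from 5.79 to 2.26 in the 4 v 8 case. In that case the row also passes the threshold of 10 events per arm for a Kaplan-Meier curve (14 v 13), which the true counts of 10 v 5 do not meet.

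**The case against.** **The number of affected cases is small and may be zero.** Patients enter without macroscopic residual or metastatic disease, and central imaging review confirms this. Recurrence leads to withdrawal from drug, and the window closes 28 days after the last dose. An RCC death must fall inside that window and be coded to a tumour term, not to something like organ failure. This stands, and it limits the size of the point. It does not make the search match the label.

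**Safety is descriptive.** SAP 7.5 plans no formal comparison between arms, the confidence intervals are wide, and no decision rule depends on this row. This also stands. The risk ratio is still a planned output and will be read as an estimate for second primaries.

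**Other tables show the truth.** Deaths are summarized by causality to the study disease (SAP 7.5.1.1), and preferred terms are displayed. These help a careful reader, but they leave the row's own estimates unchanged.

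**The list may be updated at database lock.** The stated grounds are the MedDRA version and further safety information from the axitinib program. The clause permits the correction but does not make it.

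**A stronger reading to resist.** Protocol Table 3 names further events for stopping drug: "Patients who have a grade 3 arterial event, grade 3 hemorrhagic event, grade 3 perforation/fistula", palmar-plantar erythrodysesthesia and reversible posterior leukoencephalopathy (RPLS). A reader might infer that arterial, perforation/fistula and RPLS risks are left out and never estimated. The documents do not support that:
- Arterial events fall in the cardiac, central nervous system vascular and embolism/thrombosis rows, which a footnote pools as cardiovascular disorders.
- Perforation, fistula and RPLS terms still appear with counts and percentages in the preferred-term tables (Protocol 9.4.1).
- No text requires every stop-drug event to be a special-interest category.

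What is missing is narrower: a class-level between-arm estimate for perforation/fistula and for RPLS, and a separate arterial row beside the venous one.

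**Conclusion.** The point holds as a defect of one safety row. As written, the SAP can count deaths from the study cancer as second primary malignancies and carry them into the row's risk difference, risk ratio and time-to-event display. The primary DFS analysis is not affected.

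The size is uncertain. On assumed counts of 10 v 5 true cases with 350 per arm, the risk ratio moves from 2.00 to between 1.57 and 1.08 as 3 to 12 RCC deaths are added in a 1:2 split. It moves to 1.63 with 3 v 3, and not at all if no such death occurs. These figures illustrate sensitivity and do not predict the trial's data. They rest on the search containing RCC terms, on the deaths being coded to tumour terms, and on no patient having both a second primary and a fatal RCC event in the row.

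A reader might infer that the table will hide an axitinib excess of new cancers. The documents do not show this: the number and the split of in-window RCC deaths are unknown, and the interval is wide even before any are added.

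**What to change.** **Main change, before database lock.** State in SAP 7.5.1.2 that the second-primary row excludes events that are recurrence, progression or metastasis of the RCC under study. Apply this case by case: compare each retrieved event with the recorded cause and with the secondary-malignancy determination already made for DFS. A later event in a patient whose DFS event had already occurred may have no such determination, so the serious adverse event and pathology reports would decide.

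Two shortcuts should be avoided. Restricting the row to histologically confirmed cases would lose second primaries that Protocol 7.1 accepts on imaging. Excluding all metastasis terms would lose metastases of a second primary.

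**Cost.** A short review of the retrieved cases and one added sentence. The review is best done without knowledge of treatment arm.

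**Optional and minor.** Add rows for perforation/fistula and RPLS, and an arterial row beside venous events, with the same outputs as the other rows. This costs three more safety tables. Correct the stated 13 categories: the table lists 14 rows, or 12 if the three cardiovascular rows are pooled.
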